**Preliminary studies: Reduced**

|    | P1          |            | N1          |         | P2          |         | N2          |            |
|----|-------------|------------|-------------|---------|-------------|---------|-------------|------------|
|    | Mean (SD)   | P-value    | Mean (SD)   | P-value | Mean (SD)   | P-value | Mean (SD)   | P-value    |
| PD | 0.59 (0.41) | .05 | 0.70 (0.55) | 1.0     | 0.38 (0.35) | 0.69    | 0.27 (0.24) | .02 |
|    | 1.26 (0.91) |            | 0.62 (0.31) |         | 0.34 (0.30) |         | 0.88 (0.68) |            |

Table 4. Means and standard deviations (SD) for the airway SEP (Pitts et al., 2016)

*discriminative and affective processing of airway mechanical stimuli in PD:* We have recently reported the results of our study investigating the processing of an air-puff stimulus to the posterior pharyngeal wall in people with PD. Participants were 13 people with PD, and 7 age- and sex-matched healthy older adults (controls). In both the PD and control participants we were able to successfully record SEP component peaks (Figure 7). People with PD exhibit changes to

both P1 (discriminative) and N2 (affective) peaks as compared to healthy older adults (Table 4). Specifically, people with PD over-filter the P1 and N2 peaks, indicating that there is sensory information that is prohibited from reaching the level of conscious perception and processing. A limitation of this study was that the apparatus for delivering the air puff stimulus was uncomfortable for most participants, and this may have increased attention to the stimulus, which is known to modulate the N1, P2 and N2 peaks (33). Nonetheless, this preliminary study lends support our hypothesis that discriminative and affective processing and stimulus filtering are affected in PD, however it remains unknown whether/how attention affected these results, or whether they relate to changes in the airway protective functions of cough and/or swallowing.

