## 6. Research Plan:

### **Protocol 1 (Aims 1-3)**

This prospective experimental study will include male and female adults with PD, as well as a control group consisting of healthy adults. We aim to recruit 30 participants in each group. We will recruit PD participants from the patient population at UF Fixel Institute for Neurological Diseases. Healthy control participants will be recruited from the community population, including spouses and caregivers of PD participants, as well as HealthStreet. All participants will provide written consent before enrollment into the study, which will be approved by Institutional Review Board (IRB) at the University of Florida.

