***SEP Procedures:***

Participants will be asked to refrain from strenuous physical activity, large meals and caffeine for at least four hours prior to participating. The participant will be seated in a private, sound/electrical shielded experimental room, with his or her back, neck and head comfortably supported. The participant will be monitored with a video camera. The electroencephalogram (EEG) will be collected using a 64-channel Electrical Geodesics Inc. (EGI; Eugene, Oregon, USA) net and amplifier system (amplification 20 K, nominal bandpass 0.10–100 Hz). Netstation software will be used for continuous recording of EEG data.

The 64-channel EGI electrode net will be placed on the head of the participant. Each participant will be instructed to breathe normally through a mouthpiece connected to a non-rebreathing valve. The inspiratory port will be connected to an airflow sensing pneumotachograph and inspiratory occlusion valve that obstructs the inspiratory airflow. Airflow, mouth and occlusion valve pressures will be sensed with differential pressure transducers and signal conditioners. Paired, identical inspiratory occlusions will be presented by silently inflating the occlusion valve approximately 50ms after the onset of inspiration, and will last for 150 ms. Each occlusion pair will be separated by a 500 ms interstimulus interval. The occluded breaths will be separated by at least 2 unoccluded breaths. The total time required for the presentation of the occlusions will be 700ms after the onset of inspiration, which is within the normal 1.5 second inspiratory duration. Up to 100 occlusion pairs will be delivered in each experimental trial. The latency from stimulus delivery and amplitude for the P1, N1, P2 and N2 peaks will be recorded from both the first (S1) and second (S2) occlusion.

***Attend/ignore conditions:*** In order to understand and account for the effect of attention to the stimulus on the latency, amplitude, and gating of the airway SEP peaks, we will perform the SEP procedure under 2 conditions: attend and ignore. For the attend condition, participants will be instructed to pay attention to their breathing and press a button one time whenever they feel an obstructed breath. In the ignore trial, the subject will not be given any instructions to pay attention to their breathing, and will be asked to watch a series of neutral affective pictures (IAPS; (58)) and ignore their breathing.

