***SEP outcome measures:*** *a. SEP peaks:* The latency and amplitude of the SEP P1 and N2 peaks under the attend and ignore conditions are the primary outcome variables. Secondary outcome measures include the latency and amplitude of the other component peaks, including N1 and P2 peaks. *b. SEP Gating:* The ratio of the amplitude the peaks generated by the first and second paired occlusions will be calculated for each peak, within the attend and ignore conditions. The primary outcome variable will be the ratio of S2/S1 for the P1 and N2 peaks, and the S2/S1 ratio for N1 and P2 peaks will serve as secondary outcome variables.

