## **Statistical Analysis**

**Aim 1:** A multiple regression analysis will be conducted with the slope magnitude estimation as the outcome and disease duration, age, and sex as the independent variables in addition to their mutual interaction terms. Model selection technique will be adopted to select the optimal parsimonial model deemed for the data. We will also perform subgroup analysis to

compare the slope magnitude estimation between PD patients with PAS (penetration-aspiration scale) no more than 2 and PD patients with PAS greater than 2 by adjusting confounding factors of age, gender and BMI, etc. to demonstrate that reduced slope of magnitude estimation is present in PD patients regardless of PAS status. We will include other swallow and cough outcome variables in this model to determine relationships between dependent variables.

**Aims 2 and 3:** We will first fit a multiple regression model with P1 and N2 peak amplitude and gating ratios as the dependent variable and condition (1 = attend and 2 = ignore) as independent variables by controlling confounding variables including age, gender, BMI, etc. In order to determine the relationship between P1 and N2 peaks and swallow and cough function, we will fit a second multiple regression model with P1 and N2 (amplitude and gating ratio), cough and swallow outcomes as the dependent variables and disease duration as the primary independent variable by controlling confounding variables including age, gender, BMI, etc. Also, model selection technique will be adopted to select the optimal model. Besides the primary outcomes of P1 and N2 peaks, other secondary outcomes such as N1 and P2 amplitudes and gating ratios will be analyzed.

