**Statistical analysis:** In the statistical analysis, we would fit a linear mixed effects model to take into account the repeated measurement by regarding each subject as a cluster. Specifically, in the analysis, the repeatedly measured outcome, i.e. change of penetration-aspiration scale scores (PAS), C2, cough and swallowing physiology variables from baseline, will be fitted by adjusting for fixed effects terms including baseline PAS, age, sex, medications, levodopa equivalent dose, surgical status, and disease duration (2=third 10-18 month; 1=second 10-18 month; and 0=first 10-18 month) and the random effects term due to participants. Restricted resampling model selection (Zou et al. 2015) technique will be adopted to conduct the valid statistical inference for repeated measurement data and it is also robust to missing data which is particularly useful for this study. **Expected outcomes:** Results of this aim are expected to provide a clinical deliverable in the form of sensitive and specific predictor(s) of airway protection dysfunction that are more customized for patients with different PD durations. As well, because of the study's prospective longitudinal design, this study will also be the first to examine the natural history of cough function in people with PD over the proposed 3-year time period.

**Data storage:** All participant records will be maintained in HIPPA compliant storage. Paper copies of the ICF will be kept in a locked cabinet, in the locked research laboratory of the PI (D2-063 or DG-143; [name]). Paper data collection forms will be kept in a separate, locked file cabinet, also in the research laboratory of the PI. Paper forms will not include participant names or dates; rather participants will be assigned a unique participant ID number that will be kept separate from the name. Electronic database files containing summary data for individual participants and compiled data for all participants will be saved according to participant number within a limited access, password protected folder on the PI's P-drive.

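### The first Aims 2 and 3 regression ignores that each participant is recorded under both attend and ignore; if the two values correlate positively, the attention test is conservative and loses power.

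*Combined protocol and SAP*

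**What the plan says.** The section on attend/ignore conditions (SEP Procedures, Protocol 1) states "we will perform the SEP procedure under 2 conditions: attend and ignore". It describes no allocation of different people to different conditions, so both are run in each participant. The SEP outcome measures follow from this: "The latency and amplitude of the SEP P1 and N2 peaks under the attend and ignore conditions are the primary outcome variables", and the gating ratios "will be calculated for each peak, within the attend and ignore conditions".

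The Statistical Analysis for Aims 2 and 3 starts with a multiple regression of P1 and N2 amplitude and gating ratio, taking "condition (1 = attend and 2 = ignore) as independent variables" and controlling for age, gender, BMI and unspecified further confounders. It mentions no participant effect, paired test, clustering or robust standard error.

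The plan does handle repeated measurement elsewhere. For Aim 4 (Protocol 2, Statistical analysis) it says "we would fit a linear mixed effects model to take into account the repeated measurement by regarding each subject as a cluster". Nothing carries that approach back to Protocol 1.

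**The concern.** Condition varies only within a person. A regression without a participant term leaves the stable differences between people in the residual, although those differences cancel when a person is compared with himself or herself. The advantage of measuring everyone twice is lost.

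This regression is the only stated analysis of attention. The attend and ignore conditions are there because of a limitation of the pilot study, where the apparatus was uncomfortable and may have drawn attention to the stimulus; the preliminary-studies section concedes that "it remains unknown whether/how attention affected these results". With a small sample ("We aim to recruit 30 participants in each group") and no power calculation for Aims 2 and 3, a conservative test could miss a real effect. A non-significant result might then be read as showing that attention does not matter.

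The omission acts the other way on person-level covariates, whose standard errors become too small. That matters less here, because age, gender and BMI are only adjusted for.

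**Working it through.** The plan gives no power, effect size, SD or significance level for Aims 2 and 3, so there is no figure of its own to reproduce.

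**Inputs**
- From the documents: two conditions per person; 30 participants per group, so n = 30 for one group and n = 60 for both.
- Assumed: two-sided 5% test (stated only for Protocol 2); equal variance in both conditions; one value per person per condition; within-person correlation ρ of 0.3, 0.5 and 0.7, with lower values below; attend-ignore difference d of 0.2, 0.4 and 0.6, in units of the between-person SD of a single-condition value.

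**Standard errors (SD = 1)**
- True SE of the attend-ignore difference: √(2(1−ρ)/n).
- SE reported without a participant term: about √(2/n).
- Reported/true ratio for condition: 1/√(1−ρ).
- Reported/true ratio for person-level covariates: 1/√(1+ρ).
- Actual type I error of the nominal 5% test of condition: 2Φ(−1.96/√(1−ρ)).

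| ρ | Condition SE ratio | Covariate SE ratio | Type I error, formula | Type I error, simulated n = 30 | Simulated n = 60 |
|---|---|---|---|---|---|
| 0.3 | 1.20 | 0.88 | 0.019 | 0.022 | 0.019 |
| 0.5 | 1.41 | 0.82 | 0.006 | 0.008 | 0.007 |
| 0.7 | 1.83 | 0.77 | 0.0003 | 0.001 | 0.001 |

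**Power.** 20,000 datasets were simulated per cell. Ordinary regression on condition, age, sex and BMI (2n−5 df) was compared with a paired t test (n−1 df). Each cell shows regression vs paired.

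| n | d | ρ = 0.3 | ρ = 0.5 | ρ = 0.7 |
|---|---|---|---|---|
| 30 | 0.2 | 0.08 vs 0.15 | 0.05 vs 0.19 | 0.02 vs 0.27 |
| 30 | 0.4 | 0.31 vs 0.43 | 0.29 vs 0.57 | 0.25 vs 0.78 |
| 30 | 0.6 | 0.65 vs 0.76 | 0.69 vs 0.89 | 0.74 vs 0.98 |
| 60 | 0.2 | 0.15 vs 0.25 | 0.12 vs 0.34 | 0.07 vs 0.50 |
| 60 | 0.4 | 0.61 vs 0.74 | 0.63 vs 0.87 | 0.66 vs 0.97 |
| 60 | 0.6 | 0.94 vs 0.97 | 0.97 vs 1.00 | 0.99 vs 1.00 |

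**Hand check of one cell (n = 60, d = 0.4, ρ = 0.5).** True SE = √(2 × 0.5/60) = 0.129; reported SE = √(2/60) = 0.183. Regression power = 1 − Φ((1.96 × 0.183 − 0.4)/0.129) ≈ 0.63. Paired power = 1 − Φ(1.96 − 0.4/0.129) ≈ 0.87. Both agree with the simulation.

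**Lower correlation (formulas only).** At ρ = 0.1 the condition SE is 1.05 times too large and type I error is 0.039. Power for d = 0.4 is 0.33 vs 0.37 (n = 30) and 0.60 vs 0.64 (n = 60). At ρ = 0.2 and n = 60 it is 0.60 vs 0.69. A negative correlation would reverse the direction: at ρ = −0.2 type I error is about 0.074.

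**Second regression (conditional).** The next model takes "disease duration as the primary independent variable", and the plan does not say which condition's SEP values enter it. If rows from both conditions were pooled without a participant term, simulated type I error for disease duration at n = 30 would be 0.089, 0.117 and 0.147 at ρ = 0.3, 0.5 and 0.7. Analysed at person level it is 0.049, 0.051 and 0.052. This shows what to avoid; the plan does not state that it will pool.

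**The case against.** The strongest reply is that attend versus ignore is not a study hypothesis. Hypotheses 2 and 3 concern sensory processing, filtering, disease progression and their link to cough and swallowing. The affected test errs on the safe side, its estimate is unbiased with complete pairs, and the data could be reanalysed at any time. This stands, and it limits the importance of the point. It does not remove it, because no other analysis of attention is stated.

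The size of the loss is also unknown. It depends on a correlation that the documents do not give, and the stability of an S2/S1 ratio across conditions is not known either. At a correlation of 0.1, or with a 0.6 SD effect and 60 participants, little is lost. This also stands. A positive correlation is nevertheless the ordinary expectation for the same peak in the same person.

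The plan leaves other details open. It does not say whether controls enter this model or whether both S1 and S2 amplitudes do. If both amplitudes enter, each person contributes four amplitude rows, which the simulation does not represent. These gaps affect the figures, but any such layout still has repeated values within a person.

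Finally, the open-ended covariate list might be said to leave room for a participant term. That is not persuasive: the list is of confounders, and participant is a clustering unit. The Aim 4 text shows that the authors name clustering when they intend it.

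**Conclusion.** The concern holds. Followed as written, the first Aims 2 and 3 regression gives wrong standard errors for paired data. Under positive within-person correlation, its test of attention is conservative and underpowered. The loss ranges from slight (correlation near 0.1, or a large effect with 60 participants) to severe: at a correlation of 0.7 and a 0.4 SD difference with 30 participants, power is 0.25 instead of 0.78. The direction rests on a positive correlation, and the sizes rest on the assumed correlations, effect sizes and one value per person per condition. There is no added risk of a false attention finding under positive correlation, and no bias with complete pairs. The change should be made before analysis, but the point does not undermine the study's main hypotheses.

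**What to change.** In the Aims 2 and 3 analysis, replace the first multiple regression with a linear mixed model that has a participant random intercept, keeping condition, age, gender and BMI as fixed effects. A paired attend-minus-ignore analysis is an acceptable alternative for the condition effect only, since differencing removes the person-level main effects.

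In the same edit:
- state whether controls are included and, if so, add a group term;
- state which amplitude (S1, S2 or both) is the outcome;
- state which condition's SEP values enter the second regression, and add the participant term there if both are pooled.

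The cost for the participant term is one change of wording. The data, visits and sample size stay the same, and Protocol 2 already names the method.

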### Airway sensory processing in people with PD

Central neural processing of sensory stimuli is critical for generating appropriate motor plans, and this sensorimotor relationship is disrupted in PD, resulting in many of the hallmark motor symptoms (9-11). Sensory processing involves both discriminative and affective processing components, and each is critical for generating an appropriate motor response. Discriminative processing refers to the ability to detect and gauge the intensity or magnitude of a stimulus, whereas affective processing refers to determination of stimulus characteristics, such as pleasantness or unpleasantness (4, 18). As well, sensory stimuli may be gated, or filtered, out from connecting to the sensory cortex, and this process is normal and expected for many somatosensory modalities to prevent an over abundance of redundant sensory stimuli (19, 20). Our preliminary data suggest that there are changes in both discriminative and affective processing and filtering of airwaysensation in people with PD as compared to an age- and sex-matched control group (21), however to date it is unknown whether these deficits are related to observable motor deficits of swallowing or cough. The objective of this aim is to determine whether measures of discriminative and affective processing of general airway sensation is/are associated with deficits in reflex cough and swallowing function. Further we aim to determine whether over-filtering of airway stimuli is associated with swallowing or cough deficits. Based on preliminary data we expect that people with PD will exhibit reduced discriminative processing components of airway stimuli. With disease progression, measures of affective processing components will decline and this will directly correlate with diminished reflex cough sensitivity and swallowing function. In order to achieve this objective, we will measure swallowing and cough function, reflex cough sensitivity, and the event-related sensory evoked potential (SEP) to an airway stimulus. We will compare the latency and amplitude of the SEP waveform component peaks to swallowing safety and physiology, and cough effectiveness and sensitivity, in people with PD across a range of disease durations. The rationale is that by determining the relationship between discriminative and affective processing of airway sensation and airway protective behaviors (swallowing and cough) we will better understand what type of sensory deficits are impacting airway protective function.

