## **5. Specific Aims:**

The specific aims for this project are:

Aim 1: To determine the relationships between blunted airway somatosensation, reflex cough sensitivity and effectiveness, and swallowing function in people with PD.

Hypothesis 1: We predict that blunted airway somatosensation will appear earlier (years 0 – 5 post-diagnosis) in the disease process than either cough or swallowing dysfunction, and that by 6-10 years post-diagnosis, blunted respiratory somatosensation will correlate with reduced reflexive cough sensitivity and effectiveness, and decline in swallow function and safety.

Specific aim 2: To determine whether measures of discriminative and affective processing of general airway sensation is/are associated with deficits in reflex cough and swallowing function in people with PD.

Hypothesis 2: People with PD will exhibit reduced discriminative processing components of airway stimuli. With disease progression, measures of affective processing components will decline and this will directly correlate with diminished reflex cough sensitivity and swallowing function.

Specific aim 3: To determine whether over-filtering of airway stimuli is associated with swallowing or cough deficits in people with PD.

Hypothesis 3: Over-filtering of airway stimuli will be associated with deficits in reflex cough and swallowing function in people with PD.

Aim 4: Determine the relationships between observable motor aspects of swallowing, cough, and cough sensitivity over a 3-year time period in people with PD.

Hypothesis 4: Swallowing safety and physiology in people with PD will exhibit significant differences over 3 time points, spaced 10 – 18 months apart. For people within 9 years of PD diagnosis, reduced reflex cough sensitivity will not be a sensitive and/or specific indicator of swallowing dysfunction. However, for those with a greater disease duration (10+ years), reflex cough sensitivity will be a sensitive and specific biomarker of swallowing dysfunction.

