***Voluntary cough procedure:***

Voluntary cough will be assessed using the same equipment used for reflex cough testing, without the nebulizer attached to the side port (side port is capped off). The participant will be asked to produce a sequential voluntary cough three times into the facemask attached to the pneumotachograph, and to maintain a comfortable seated position for all cough testing. Each cough trial will be separated by approximately 1 minute of quiet breathing. Participants will be given the following instructions for cough production: “When you are ready, cough as if something has gone down the wrong pipe.”

**Cough outcome variable:** The concentration of capsaicin that elicits the 2-cough response (C2) will be recorded and serve as our measure of cough reflex sensitivity. Additionally, airflow measurements will be derived from the reflex and voluntary cough waveforms. Measurements will include compression phase duration (CPD), peak expiratory flow rate (PEFR), and peak expiratory flow rise time (PEFRT) and cough volume acceleration (CVA=PEFR / PEFRT).

**Urge-to-cough (UtC):** Following each capsaicin trial participants will rate their urge-to-cough (UtC) on a modified Borg rating scale, where 0 is no UtC, and 10 is maximal UtC. The UtC provides information regarding participants’ perceived magnitude of the stimulus.

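### Aims 2 and 3: the model meant to relate P1 and N2 to cough and swallowing estimates each measure's relation to disease duration, not their association

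*Combined protocol and SAP*

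**What the plan says.** Under Specific Aims, Aim 2 asks whether discriminative and affective processing measures are associated with reflex cough and swallowing deficits. Hypothesis 2 adds: "With disease progression, measures of affective processing components will decline and this will directly correlate with diminished reflex cough sensitivity and swallowing function". Aim 3 is: "To determine whether over-filtering of airway stimuli is associated with swallowing or cough deficits in people with PD".

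The Statistical Analysis section of Protocol 1 gives two regressions for these aims.

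- The first has P1 and N2 amplitude and gating ratio as outcomes and the attend/ignore condition as predictor. It contains no cough or swallow variable.
- The second is introduced with this purpose: "In order to determine the relationship between P1 and N2 peaks and swallow and cough function". Its outcomes are P1 and N2 (amplitude and gating ratio) together with "cough and swallow outcomes as the dependent variables and disease duration as the primary independent variable", controlling for age, gender, BMI and the like.

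Two other statements come close. The Aim 1 paragraph says: "We will include other swallow and cough outcome variables in this model to determine relationships between dependent variables". The Background says: "We will compare the latency and amplitude of the SEP waveform component peaks to swallowing safety and physiology, and cough effectiveness and sensitivity". On size, Protocol 1 states: "We aim to recruit 30 participants in each group".

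**The concern.** The stated purpose and the stated terms of the second regression do not match. The purpose is an association between two sets of measures, SEP and function. The terms place both sets on the outcome side and relate each to disease duration. The resulting coefficients address the progression part of Hypothesis 2, that measures decline as disease advances. They do not address whether a patient with a weaker P1 or N2 also has poorer cough or swallowing.

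Two measures can both worsen with duration and have no link beyond it. They can also be closely linked and unrelated to duration, which Aim 3 leaves open because it has no duration premise. The duration coefficients do not separate these situations. With no SEP-function estimate named, the choice of peak, condition, outcome and adjustment falls to the analyst after the data are in.

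**Working it through.** **Terms of the models.** The plan gives no figure for Aims 2 and 3 to reproduce, so the check starts with structure. Write S for an SEP measure, F for a cough or swallow measure, D for duration and Z for the confounders. The second regression amounts to

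S = a₁ + b₁D + c₁Z + e₁ and F = a₂ + b₂D + c₂Z + e₂.

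The association given duration is corr(e₁, e₂). The named primary coefficients are b₁ and b₂, and neither depends on corr(e₁, e₂).

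**Large-sample check (assumed values, n = 200,000).** Set b₁ = −0.5, b₂ = +0.5, one confounder with coefficient 0.2 in both equations, and unit residual variance. The overall correlation is then (−0.25 + 0.04 + ρ)/1.29, where ρ = corr(e₁, e₂).

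| ρ set | Fitted b₁, b₂ | Recovered adjusted correlation | Overall correlation |
|---|---|---|---|
| −0.6 | −0.50, 0.50 | −0.60 | −0.63 |
| 0 | −0.50, 0.50 | 0.00 | −0.16 |
| +0.6 | −0.50, 0.50 | 0.60 | 0.30 |

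The duration coefficients are the same in all three rows.

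**At the planned size.** Inputs: 30 PD participants (Protocol 1). Assumed: normal measures, adjustment for age, sex and BMI, two-sided 0.05, 10,000 runs per row. For the case closest to Hypothesis 2, each measure is correlated 0.5 with duration, so the overall correlation is 0.25 + 0.75ρ. The mean rate per duration coefficient is (both + at least one)/2.

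| ρ given duration | Overall correlation | Both duration coefficients p<0.05 | At least one | Mean per coefficient | Direct test, adjusted for duration | Direct test, not adjusted |
|---|---|---|---|---|---|---|
| 0 | 0.25 | 62.6% | 94.4% | 78.5% | 5.1% | 24.1% |
| 0.3 | 0.475 | 64.2% | 91.8% | 78.0% | 31.9% | 72.7% |
| 0.5 | 0.625 | 66.7% | 89.9% | 78.3% | 76.3% | 95.4% |
| 0.7 | 0.775 | 69.4% | 87.0% | 78.2% | 98.8% | 99.8% |

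Each duration coefficient is significant in about 78% of runs, whatever the association given duration.

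If S and F are correlated 0.3/0.5/0.7 but unrelated to duration, at least one duration coefficient is significant in 9.2/9.5/8.7% of runs and both in 0.4/0.9/1.5%. The mean per coefficient is 4.8/5.2/5.1%, which is the chance level. The direct adjusted test gives 32/77/99%.

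**Precision of a direct estimate.** With four adjusting covariates, the standard error on the Fisher z scale is 1/√(30 − 3 − 4) = 0.209.

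- Power for a partial correlation of 0.3: Φ(0.310/0.209 − 1.96) ≈ 0.32.
- Partial correlation detectable with 80% power: tanh((1.960 + 0.842) × 0.209) ≈ 0.53.
- 95% interval around an observed 0.30: about −0.10 to 0.62.

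**The case against.** The strongest defence is that the second regression is a joint multivariate model. It lists several dependent variables together and has the SEP-function relationship as its purpose. In that linear model the residual correlation is the duration-adjusted association: its p-value matched that of the direct adjusted test in all 100,000 simulated runs. This reading is plausible, and under it one clarifying sentence would be enough. But the text says multiple regression and states neither a joint fit nor that readout. The Aim 1 sentence on relationships between dependent variables refers to the Aim 1 model, and the Background sentence gives intent without a method.

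Two stronger readings are tempting, and the documents support neither.

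- A reader might infer that the duration coefficients will be reported as the SEP-function relationship, so that false links are claimed and real ones missed. The plan does not say this. The rules of both, or at least one, coefficient being significant are devices of the illustration, not the plan's decision rules.
- A reader might infer that only the duration-adjusted association is valid. Hypothesis 2 ties the correlation to progression, so association arising through duration is arguably part of it. The unadjusted 24% in the top row is then power for a real overall correlation of 0.25, not a false-positive rate. Adjustment also costs power: 32% against 73% at a partial correlation of 0.3.

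Nor can a chance-finding rate be attached to the open choice of tests, because the documents do not fix how many would be run.

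**Conclusion.** The point stands as a mismatch between stated purpose and stated terms. The coefficients named for Aims 2 and 3 do not estimate the association that these aims, and the correlation part of Hypothesis 2, ask about. This is more than missing detail, because the model offered for the purpose answers another question. The structural conclusion needs no assumed effect size. The percentages do: they rest on assumed correlations, normal measures and 30 PD participants, and they show scale only. The firm consequence is that the estimate, and whether duration is adjusted for, remain open until after the data are seen. The correction is one of wording and should be made before analysis.

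**What to change.** Keep the duration models for the progression part of Hypothesis 2. Add, in PD participants, a direct model of a cough or swallow outcome on the SEP measure, adjusted for age, sex and BMI:

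- **Outcomes:** C2, of which the plan says "The concentration of capsaicin that elicits the 2-cough response (C2) will be recorded and serve as our measure of cough reflex sensitivity", and PAS, its primary swallowing outcome.
- **SEP measures:** P1 and N2 amplitude for Aim 2; the P1 and N2 S2/S1 ratios for Aim 3.
- **Method:** rank-based partial correlation or ordinal regression, because C2 takes a few set concentrations and PAS is ordinal. State how participants who never reach C2 are ranked. With an assumed five-category outcome, the duration-adjusted rank test held about 5% under no association and had 25–28% power at a correlation of 0.3. A proportional-odds likelihood ratio test rejected in 7–9% under no association (1,000 runs), so it would need a small-sample check.
- **Reporting:** estimates with confidence intervals, with and without duration adjustment. The unadjusted version includes association through progression; the adjusted version does not.
- **Stated in advance by the investigators:** which version, attend/ignore condition and peak-outcome pair is primary for each aim. All others are secondary.

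If a joint model was meant, say so and name the residual correlation as its readout. Its equality with the direct test holds for the linear model, not for the rank-based one.

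Before N2 is named as the affective measure, reconcile its role. The Background's description of the SEP peaks assigns N2 to higher order cognitive processing, whereas the preliminary-studies text labels it affective.

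The cost is SAP wording, with the same data and standard software. The downsides are a few more tests, which is why primaries must be named, and the low precision shown above.
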